### 5.9.2 *Cross-Sectional Imaging*

All scheduled CT and MR studies will be assessed by a central core lab neuroradiologist. The volume of hemorrhage on the diagnostic scan will be calculated using a standard  $A \times B \times C/2$  calculation. On the CT slice with the largest area of ICH, the largest diameter (A) is measured in cm. The dimension of the hemorrhage perpendicular to the largest diameter (B), represents the second diameter. The third diameter (C) will be calculated either by multiplying the number of CT slices which depict the hematoma by the slice thickness or determined on coronal or sagittal reconstructions.

Hemorrhage volumes will also be assessed using a manual volume measurement technique on the diagnostic scan and all subsequent scans, as defined in the Imaging Manual. Intraventricular hemorrhage will be assessed on each scan and graded according to a modified Graeb score (see the Imaging Manual and Manual of Procedures).

Scheduled imaging studies include the diagnostic/admission scan, the stability scan(s) (at least 6 hours after the diagnostic scan), CT or MR angiogram (with either the diagnostic or stability scan), Post-operative post-presentation scan 7 day post presentation scan.

Table 1. Schedule of Events

ACTIVITY	SCREENING /BASELINE	STABILITY SCAN (at least 6 hours post initial CT)	TREATMENT	24 hour post - MIES (+/-12)	DISCHARGE AND/OR 7 DAYS (+/- 1 day)	3 MONTHS (+/- 14 days)	6 MONTHS (+/- 21 days)	1 YEAR or END OF STUDY (+/- 35 days)
Informed Consent	X							
Inclusion/ Exclusion Criteria	X							
Medical History	X							
Focused Exam	X	X		X	X	X	X	X
Standard of Care Labs	X	X		X	X			
Standard of Care CT/MR	X	X	X		X			
CTA or MRA	X (or at stability)	X (if not done with Baseline)						
Barthel	Historic					X	X	X
NIHSS	X	X		X	X	X	X	X
GCS	X	X		X	X	X	X	X
mRS	Historic			X	X	X	X	X
Stroke Impact Scale (QOL)						X	X	X
ED-5D-5L						X	X	X
Pregnancy Test if childbearing potential	X	Or X						
Con Medications	X	X	X	X	X	X	X	X
Apollo / Artemis MIES under general anesthesia within 24 hours of sx onset			X					
Adverse Events			X	X	X	X	X	X
All brain imaging sent to central core lab	within 48 hours of test	within 48 hours of test	within 48 hours of test	within 48 hours of test	within 48 hours of test			

### 5.9.3 *Serious Adverse Events*

All serious adverse events occurring during the 365 days of study participation will be recorded. Adverse events and serious adverse events are critical endpoints and will be assessed as they occur and at the scheduled clinic visits. A serious adverse event is one that is fatal or life-threatening, is permanently or substantially disabling, requires or prolongs hospitalization, or any event that the treating clinician judges to be a significant hazard. For each recorded serious adverse event, the patient's attending physician will be asked to classify the causal relationship of the event to the study treatment as probable, possible, unlikely, and unrelated. Detailed form and narrative reports of the following specific adverse events will be obtained:

- Death (all cause) within 90 days of enrollment
- Death within 7 days of enrollment: Immediate periprocedural death
- Symptomatic Re-Hemorrhage or New Hemorrhagic Event: any new intracranial hemorrhage or increase in size of pre-existing hemorrhage (IPH, IVH or extra-axial bleed) within 90 days associated with an increase of 4 or more points on the NIHSS or GCS increase  $\geq 2$  persisting for at least 24 hours and/or requiring emergency surgical decompression or resulting in death.
- Symptomatic Evolution of Perihematomal Edema: Edema with increased mass effect or uncontrolled ICPs within 90 days requiring emergency surgical decompression NOT related to new or increased hemorrhage (i.e. edema related) associated with an increase of 4 or more points on the NIHSS or GCS increase  $\geq 2$  persisting for at least 24 hours, and/or requiring emergency surgical decompression or resulting in death.
- Symptomatic Ischemic Stroke: A new ischemic stroke (ipsilateral, contralateral; contiguous with bleed/operative site or remote; cortical, subcortical or perforator distribution) within 90 days associated with an increase of 4 or more points on the NIHSS or GCS increase  $\geq 2$  persisting for at least 24 hours and/or requiring emergency surgical decompression or resulting in death.
- Surgical complications related to Apollo / Artemis MIES: Surgical site infection, brain abscess or confirmed meningitis, or documented complication(s) deemed specifically related to the procedural anesthetic (medication, access or intubation related) within 90 days.

A medical monitor will review these specific categories of events as they are reported. The DSMB will also function as the CEC and will review all of these specified categories of events at regularly scheduled DSMB meetings, which will occur at approximately 6-month intervals during the study. The medical monitor has the authority to alert the DSMB at any time if a potential safety issue arises. If at any point, these reviews raise any safety concerns, the DSMB will be empowered to suggest that the trial be placed on hold and request additional analyses of the trial dataset. The DSMB will issue reports for each meeting. The DSMB will be composed of three cerebrovascular specialists and a statistician. Safety stopping rules for the primary safety endpoint will be developed and used to help the DSMB make its safety assessments. Additional details of the monitoring plan will be included in the study MOP. Additional details regarding the DSMB structure and stopping rules will be included in the DSMB charter.

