### ***The Case for Minimally Invasive Hematoma Evacuation***

The failure of conventional surgical evacuation to improve outcomes in ICH has been attributed to the morbidity associated with the craniotomy and surgical approach. Specifically, it has been proposed that the surgical approach to the hematoma may cause enough damage to surrounding brain to offset any potential benefits of surgery. Correspondingly, it is possible that the potential benefits of hematoma evacuation could be realized if the procedure could be performed through a minimally invasive access.

A large meta-analysis of surgical treatment strategies for ICH concluded that surgery could be beneficial in patients undergoing early surgery (within 8 hours), with moderately sized hemorrhages (20-50cc), of moderate age (50 – 69 years) and with moderate to severe clinical deficits (GCS 9 – 12). Incidentally, an evaluation of the contributing data sets indicates that a single study (Wang et al.) largely drove the clinical benefit in each of the cohorts.

Wang et al. conducted a randomized trial in 465 patients with intracranial hemorrhage, randomizing patients between medical management and minimally invasive craniopuncture therapy. The craniopuncture procedure consisted of the CT-guided placement of a puncture needle into the hematoma. Following the aspiration of hematoma fluid, a lysis fluid (containing urokinase) was injected under pressure into the hematoma. The drainage needle was secured into position and allowed to drain for 3-5 days after placement. Using this technique, the authors reported a significant improvement in clinical outcomes with 41% of the craniopuncture group and 63% of the medical management group being dependent (mRS > 2) 90 days.

This minimally invasive CT-guided craniopuncture technique is routinely practiced in China with over 150,000 patients undergoing this procedure yearly. Zhou reported a meta-analysis of 12 studies including 1955 patients randomized between medical management and minimally invasive surgery. These investigators reported robust reductions in both death (46% relative risk reduction) and death or dependence (47% relative risk reduction) at the end of follow-up in patients undergoing MIS (minimally invasive surgery).

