## **Rationale for the INVEST Feasibility Design**

The INVEST feasibility study was designed to include those patients who theoretically hold the highest potential to benefit from the Apollo or Artemis MIES procedure and thereby assess our ability to recruit and follow this patient population, which has been identified to maximize the odds of potentially observing a treatment effect in subsequent RCTs. Specific components of the design are addressed below.

**Patients with presenting GCS of  $\leq 4$  have been excluded from the INVEST feasibility study.** Patients with very low GCS (3-4) represent a heterogeneous group and many will have severe, unrecoverable injuries potentially involving the brain stem. While some in this group may, in fact, benefit from the Apollo or Artemis MIES procedure, it is likely that majority will not. Furthermore, this severely injured patient population will likely have substantial barriers to follow up and may limit long-term data collection. As such, these patients are excluded from the INVEST feasibility study so as not to include a population that might eventually dilute any evidence of a potential treatment effect in a subsequent RCT. At the same time, if experienced operators at INVEST centers identify individual patients in this group whom they feel will benefit from the Apollo or Artemis MIES procedure and intend to treat the patients outside of the INVEST feasibility study, these patients may be eligible for enrollment in the companion INVEST single-arm observational registry (see accompanying protocol).

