## **5.9 Follow-Up Examination**

### **5.9.1 Clinical**

Several clinical outcome measures were selected for this study. These were chosen on the basis of their reliability, familiarity to the neurologic community, adaptability for use in patients who have had a stroke, and comparability to end points used in other trials of intracranial hemorrhage. All scores will be recorded in electronic case report forms as well as within the medical record and/or in research source documentation as appropriate.

1. Modified Rankin Scale: mRS is an overall assessment of global handicap. In the original Rankin Scale, a score of zero indicates the absence of symptoms and a score of 5, severe disability. The modified Rankin Scale adds a score of 6 for fatal outcomes. A historical mRS will be obtained to assess the patient's level of function prior to the ICH. The score will be repeated as specified in Table 1.

2. Barthel Index: The Barthel Index is an ordinal scale used to measure performance of activities of daily living. A historical Barthel Index score will be obtained to assess the patient's level of function prior to the ICH. The score will be repeated as specified in Table 1.
3. The National Institutes of Health Stroke Scale is a 42-point scale that quantifies neurologic deficits in 11 categories. Normal function without neurologic deficit is given a score of zero. NIHSS should be done by a certified examiner as close to the specified times as possible.
4. EQ-5D-5L is a standardized instrument for use as a measure of health outcome. Applicable to a wide range of health conditions and treatments, the questionnaire provides a simple descriptive profile and a single index value for health status.
5. Stroke Impact Scale: Additionally a quality of life scale outcome measure will be utilized in this study. Quality of life scales are designed to be sensitive to changes in outcome from mild and moderate stroke undetected by other outcome measures. Important parameters not fully interrogated by conventional outcome scales can be assessed by quality of life scales, including emotion, communication, cognition, and social role function. Standard measures, such as the mRS, primarily evaluate physical aspects of stroke outcome, not addressing more relevant quality of life measures. The Stroke Impact Scale is a validated assessment of quality of life specifically in patients with stroke.  
45 45 4547

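### The worsening trigger for three named safety events asks for a GCS increase, which is improvement, so re-hemorrhage and ischemic stroke can be misclassified in both directions

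*Combined protocol and SAP*

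**What the plan says.** Section 5.9.3 lists specific adverse events that need a detailed form and narrative. Three of them depend on a neurological change: symptomatic re-hemorrhage, symptomatic evolution of perihematomal edema, and symptomatic ischemic stroke. In each, the event must be "associated with an increase of 4 or more points on the NIHSS or GCS increase" of 2 or more, persisting for at least 24 hours. Emergency surgical decompression or death is offered as a further route. Section 7.5.2.1 repeats the three definitions almost unchanged, for events that the medical monitor assesses and that are presented to the TOC and DSMB.

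The stems of the definitions differ:

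- Re-hemorrhage covers "any new intracranial hemorrhage or increase in size of pre-existing hemorrhage", with no minimum volume.
- Edema reads "Edema with increased mass effect or uncontrolled ICPs within 90 days requiring emergency surgical decompression NOT related to new or increased hemorrhage", and decompression then appears a second time at the end as an alternative.

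On oversight, Section 5.9.3 says "The DSMB will also function as the CEC and will review all of these specified categories of events". It also says "Safety stopping rules for the primary safety endpoint will be developed". Section 7.5.1 names death within 90 days as the primary safety outcome.

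**The concern.** The NIHSS and GCS limbs are offered as alternative signs that the patient has worsened, but the two scales run in opposite directions. A rise in NIHSS is deterioration and a rise in GCS is recovery. Read literally, the GCS limb admits patients who are improving and leaves out patients who are deteriorating.

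What is at stake is correct assignment to the re-hemorrhage and ischemic stroke categories. These lead to narratives, medical-monitor review and adjudication by the DSMB in its CEC role. Re-bleeding is also a procedural risk that the protocol itself quantifies, at 2 of 29 patients in Section 2.1. If some sites apply the text literally while others, or the adjudicators, silently reverse it, the categories will not be consistent across up to 10 centers.

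**Working it through.** The plan gives no figure to reproduce here. The check is of scale direction, followed by a count of the classifications that change.

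**1. Direction of each scale in the protocol's own terms**

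- NIHSS (Section 5.9.1): "Normal function without neurologic deficit is given a score of zero". An increase is worsening, so this limb is correctly directed.
- GCS (Rationale for the INVEST Feasibility Design): "Patients with very low GCS (3-4) represent a heterogeneous group and many will have severe, unrecoverable injuries potentially involving the brain stem". The Case for Minimally Invasive Hematoma Evacuation also describes a GCS of 9 to 12 as a moderate-to-severe deficit. Low is bad, so an increase is improvement.
- No section words the GCS limb as a decrease.

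**2. Number of places**

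3 definitions × 2 sections (5.9.3 and 7.5.2.1) = 6 occurrences.

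**3. Which patients change class**

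Take a patient who already has the qualifying bleed or stroke, and assume any score change lasts at least 24 hours. Cross NIHSS rise of 4 or more (yes/no), GCS (fall of 2 or more, no such change, rise of 2 or more) and decompression or death (yes/no): 2 × 3 × 2 = 12 combinations.

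In 9 of the 12, an NIHSS rise of 4 or more, or decompression or death, is present, and the event is met whatever the GCS does. The other 3 have neither:

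| GCS change | As written (increase) | Read as a decrease |
|---|---|---|
| Fall of 2 or more | Not an event | Event |
| No such change | Not an event | Not an event |
| Rise of 2 or more | Event | Not an event |

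So 2 of 12 combinations change, one in each direction, and 10 do not. These are combinations, not patients. The documents give no frequencies for them.

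**4. Room for the false-positive case**

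Entry GCS is 5 to 15 (Section 4.1). From the entry score, anyone at 13 or below can rise by 2 without passing 15.

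**5. Edema**

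If the stem makes decompression mandatory, every edema event already has decompression and the GCS direction changes nothing. The practical effect is then on 2 of 3 categories, or 4 of the 6 occurrences. If decompression is only one alternative, edema is affected as well. The text supports either reading.

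**6. Scale**

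With 50 patients (Section 7.1), one patient is 1/50 = 2.0 percentage points. Exact (Clopper-Pearson) 95% intervals:

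- 0/50: 0 to 7.1% (upper limit = 1 − 0.025^(1/50) = 0.0711)
- 1/50 = 2%: 0.05% to 10.7%
- 3/50 = 6%: 1.3% to 16.5%
- 4/50 = 8%: 2.2% to 19.2%

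The earlier re-bleeding rate of 2/29 = 6.9%, carried to 50 patients, gives 50 × 2/29 = 3.4 expected re-bleeds. At counts this low, one misassigned patient is visible. The intervals show only what one event is worth; they do not measure the error.

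**The case against.** The strongest reply is that this is an obvious slip with little consequence. Each definition is headed as symptomatic, the NIHSS limb beside it states worsening, and the adjudicators include three cerebrovascular specialists who would hardly count a patient because consciousness improved. On the other side, a missed case needs a GCS fall of 2 or more with an NIHSS rise below 4, no decompression and no death. Such a case reported as an SAE is not lost: Section 16.2 sends serious events to the medical monitor for independent review, Section 9 has the DSMB review all adverse events periodically, and Section 7.5.2.1 gives the DSMB and TOC reports of all AEs and SAEs. No rate analysis is planned for these categories, and the manual of procedures, DSMB charter and case report forms, which may word the rule correctly, are not available here.

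Much of this stands and limits the consequence. A missed case reported as an SAE still reaches the people who oversee safety. What it can lose is the category label, the detailed form and narrative, and adjudication under that heading. But expecting every site and adjudicator to reverse a written rule in the same way is not a safeguard, and nothing in the protocol corrects the text.

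A further objection is that scheduled GCS assessments may not be enough to re-check past events, because the definition needs a change lasting 24 hours and names no reference assessment. That is fair, but the same difficulty exists under the present wording. Reversing the direction does not add to the data required.

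**Conclusion.** The concern holds. The GCS limb is wrong as written in all six places. It misclassifies in both directions, but only where the NIHSS rise is below 4 and there is neither decompression nor death. Re-hemorrhage and ischemic stroke are affected; edema is affected only if decompression is not a required element.

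The number of patients involved cannot be estimated, because the documents do not say how often a bleed or stroke is accompanied by a 2-point GCS change without a 4-point NIHSS rise. The 90-day death outcome, the stopping rules planned for it and the feasibility endpoints do not depend on this trigger. The conclusion rests on the literal text and on the protocol's own use of the two scales; whether the wording reached the operational forms is unknown. It should be fixed because it is an operative rule for named safety categories, not because it threatens the trial's main results.

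**What to change.** - Replace the GCS increase with a GCS decrease, at the existing threshold of 2, in all three definitions in Section 5.9.3 and all three in Section 7.5.2.1.
- Check the case report forms, manual of procedures and DSMB charter for the same wording and align them.
- Re-check any events already classified, in both directions: bleeds and strokes counted on a rising GCS, and those left out despite a falling one.
- Reconcile the edema definition in both sections, so that it is clear whether emergency decompression is required or is one of several alternatives.
- While the text is open, state the assessment from which NIHSS and GCS changes are measured; the definitions do not name one.

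The cost is one word in six places and one clarified clause in two sections, plus the reference assessment. GCS and NIHSS are already collected at the scheduled visits (Table 1; Section 5.7.1 for discharge), so the change of direction adds no assessment. The real work is the re-check, which may need scores recorded around the time of the event as well as those from scheduled visits.

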### **2.1 Risk Analysis**

The primary risks to subjects in this study are associated with the minimally invasive surgical procedure and the associated general anesthetic. Imaging performed throughout the course of the study, while specified in the protocol, falls well within the standard of care for the initial evaluation and follow-up of patients with intracranial hemorrhage. The Apollo or Artemis MIES procedure is performed in a manner, which is similar to that of other neuroendoscopic procedures, and the associated risks are likewise similar. In brief (see Section 5 for a detailed description of the procedure), the Apollo/Artemis MIES procedure itself involves the creation of a mini-craniectomy and dural incision. An endoscopic sheath (19-22F) is then placed through this access site into the hematoma under imaging control using neuronavigation. Then, under endoscopic guidance, the hemorrhage is evacuated with the Apollo system or Artemis Device. Following the evacuation, the endoscope and Apollo system or Artemis Device are removed.

Control intraoperative (as specified in Section 5) CT imaging is performed to assess the remaining hemorrhage volume and to assess for immediate procedural complications. Based on the intra-operative control CT imaging, either an additional pass(es) is made, or the procedure is terminated. Following the procedure, all equipment is removed and the cranial access is closed in a standard manner.

Risks related to the procedure include bleeding, infection or damage to surrounding structures during the creation of the cranial access or placement of the sheath. These risks are all unlikely and are estimated to occur in less than 5% of cases. During evacuation of hemorrhagic products with the Apollo system / Artemis Device, there is the possibility of inducing or encountering additional hemorrhage in the operative bed. In a retrospective multicenter study of the Apollo / Artemis procedure for the treatment of ICH, re-bleeding was encountered in 2 of 29 patients (6.9%). The risk related to the general anesthetic in this patient population is estimated to be approximately 1-5% for major morbidity and mortality (e.g. airway management issues, aspiration, hypotension or drug reaction), given

that their American Society of Anesthesiologists (ASA) score would typically be 4 or 4e in this category of patients.

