#### **7.5.2 *Interim Safety Monitoring***

##### **7.5.2.1 *Stopping the Trial Based on Interim Safety Data***

The Trial Operating Committee (TOC) and Data Safety Monitoring Board (DSMB) will receive periodic safety reports of all AEs and SAEs. In addition, the following specific endpoints will be assessed by the medical monitor and presented:

- Death (all cause) within 90 days of enrollment
- Death within 7 days of enrollment: Immediate periprocedural death

- Symptomatic Re-Hemorrhage or New Hemorrhagic Event: any new intracranial hemorrhage or increase in size of pre-existing hemorrhage (IPH, IVH or extra-axial bleed) within 90 days associated with an increase of 4 or more points on the NIHSS or GCS increase  $\geq 2$  persisting for at least 24 hours and/or requiring emergency surgical decompression or resulting in death.
- Symptomatic Evolution of Perihematomal Edema: Edema with increased mass effect or uncontrolled ICPs within 90 days requiring emergency surgical decompression NOT related to new or increased hemorrhage (i.e. edema related) associated with an increase of 4 or more points on the NIHSS or GCS increase  $\geq 2$  persisting for at least 24 hours and/or requiring emergency surgical decompression or resulting in death.
- Symptomatic Ischemic Stroke: A new ischemic stroke (ipsilateral, contralateral; contiguous with bleed/operative site or remote; cortical, subcortical or perforator distribution) within 9s associated with an increase of 4 or more points on the NIHSS or GCS increase  $\geq 2$  persisting for at least 24 hours and/or requiring emergency surgical decompression or resulting in death.
- Surgical complications related to Apollo / Artemis MIES: Surgical site infection, brain abscess or confirmed meningitis, or documented complication(s) deemed specifically related to the procedural anesthetic (medication, access or intubation related) within 90 days.

Additional details of the monitoring plan will be included in the study MOP. Additional details regarding the DSMB structure and stopping rules will be included in the DSMB charter.

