### **16.2            *Reporting and Review of Adverse Events***

To provide for consistent reporting of adverse events, serious and non-serious adverse events will be recorded on the Adverse Event CRF. Non-serious adverse events will be recorded from enrollment through Day 7 or hospital discharge (whichever occurs first). Serious adverse events will be recorded from enrollment through the end of study (i.e., 90 day final follow-up visit, death, or withdrawal of consent).

In order to ensure prompt reporting of adverse events, we require that all adverse events be entered into the REDCap web-based database (REDCap) within five working days of their becoming aware of the event during the initial admission. For all serious adverse events (SAEs), we require that they be reported in the REDCap within 24 hours of the study site staff first being made aware of the occurrence of the SAE. The 24- hour reporting requirement for SAEs applies to all study phases.

Reporting of serious or life-threatening adverse events will trigger notification of the event to the Medical Monitor (MM). The MM will conduct an independent review of these specific SAE. If the MM believes the adverse event is serious, unexpected and either definitely, probably, or possibly related to the investigational device(s) and/or study procedures, the TOC staff will forward a Safety Report (pre-filled with as much data as possible) to the clinical site Investigator to be completed with any additional information that may be relevant to the SAE. The Safety Reports will be included in the reports prepared for the DSMB. The principal investigator, at each clinical site, will be responsible for reporting to his/her own IRB/EC according to individual IRB/EC policies. After the submission of the initial Safety Report, the principal investigator at the corresponding clinical site will be responsible for obtaining follow-up information about the event, in order for it to be reported it to the TOC.

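### Surgical site infection is a named event to day 90, but non-serious events stop being recorded by day 7; sub-threshold re-bleeding and access-path deficits fall under no named event

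*Combined protocol and SAP*

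**What the plan says.** Section 2.1 (Risk Analysis) sets out the hazards of the operation: "Risks related to the procedure include bleeding, infection or damage to surrounding structures during the creation of the cranial access or placement of the sheath". It adds that "These risks are all unlikely and are estimated to occur in less than 5% of cases". For hemorrhage during evacuation it cites a retrospective multicenter series in which "re-bleeding was encountered in 2 of 29 patients (6.9"%).

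Section 5.9.3 lists specific events for which a detailed form and a narrative are obtained. They are death within 90 days, death within 7 days, symptomatic re-hemorrhage or new hemorrhage, symptomatic perihematomal edema, symptomatic ischemic stroke, and surgical complications. The last is defined as "Surgical site infection, brain abscess or confirmed meningitis, or documented complication(s) deemed specifically related to the procedural anesthetic (medication, access or intubation related) within 90" (in days). Section 7.5.2.1 repeats it: "Surgical complications related to Apollo / Artemis MIES: Surgical site infection, brain abscess or confirmed meningitis", and so on. The medical monitor reviews these categories as they are reported, and the DSMB, acting also as the CEC, reviews them at its meetings.

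On collection, Section 16.2 says: "Non-serious adverse events will be recorded from enrollment through Day 7 or hospital discharge (whichever occurs first"). Section 16 has the same limit. Section 5.9.1 has each visit survey the record, and ask the patient or representative, for neurological adverse or serious adverse events, with a further question about neurosurgical procedures. Table 1 marks Adverse Events at every column from treatment to one year.

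**The concern.** Two things do not fit together.

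First, one named event runs for 90 days, but the general recording rule stops after at most 7 days for anything non-serious. Brain abscess and meningitis would ordinarily be serious and so are recorded well past day 7. A superficial wound infection treated as an outpatient in week 2 or 3 would ordinarily not be serious. A site that follows Section 16 does not record it, and a site that follows 5.9.3 does. Ascertainment could then differ between sites for a category sent to the medical monitor and the DSMB.

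Second, the list of named events does not cover all the hazards in Section 2.1. Bleeding appears only when it is symptomatic, needs emergency decompression or is fatal. Damage to surrounding structures appears only when it shows as a qualifying hemorrhage, infarct or edema event. The rest has no definition, narrative or specified review, so it cannot give a consistent count. The study is meant to inform later trials, and the only procedural complication figure in the protocol with a numerator and denominator is the 2/29. That figure carries no symptomatic qualifier, so the trial's own hemorrhage event does not measure the same thing.

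**Working it through.** **Recording windows, side by side**

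- Surgical site infection as a named event: 90 days from enrollment (5.9.3, 7.5.2.1).
- Non-serious adverse events: at most 7 days, less if discharge is earlier (16, 16.2).
- Serious adverse events: 90 days by Sections 16 and 16.2, 365 days by 5.9.3. These two also need reconciling, but either one covers the 90-day event.
- Visit survey: neurological events and neurosurgical procedures only (5.9.1).

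The conflict is therefore confined to non-serious events. Calendar time outside the Section 16 window: 90 - 7 = 83 days at least, or 83/90 = 92%. This is time, not risk; the documents do not say when infections occur.

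Illustration, on assumed figures only: with a 90-day risk of non-serious surgical site infection of 1% to 5%, and 25% to 75% of cases arising after the window closes, the number unrecorded in 50 patients is

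- low end: 50 x 0.01 x 0.25 = 0.1
- high end: 50 x 0.05 x 0.75 = 1.9

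If 5.9.3 governs, the number is 0.

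**Coverage of the Section 2.1 hazards**

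- Infection: in the surgical complications event.
- Bleeding with sustained worsening, emergency decompression or death: in the re-hemorrhage event.
- Bleeding below that threshold: in no named event.
- Injury appearing as a symptomatic infarct, including one contiguous with the operative site: in the ischemic stroke event.
- Injury causing a new deficit without new blood, infarct or qualifying edema: in no named event. The word access in the surgical complications definition sits in a parenthesis about the anesthetic, so it does not bring in cranial access.

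**The re-bleeding figure**

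Inputs: 2 of 29 (Section 2.1); up to 50 patients (Section 7.1).

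- Reproduced: 2/29 = 0.069, or 6.9%.
- Exact (Clopper-Pearson) 95% CI: 0.8% to 22.8%.
- Expected in 50 patients: 50 x 2/29 = 3.4.
- Chance of at least one: 1 - (27/29)^50 = 0.97.

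Let s be the share of re-bleeds below the symptomatic threshold. The documents give no value, so s runs from 0 to 1. The number in no named event is 3.4 x s:

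| s | patients of 50 |
|---|---|
| 0 | 0 |
| 0.25 | 0.9 |
| 0.5 | 1.7 |
| 0.75 | 2.6 |
| 1 | 3.4 |

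No comparable figure can be worked out for access-path deficits. Section 2.1 gives only a bound of 5%, for bleeding, infection and structural damage together.

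**The case against.** The best defense is that separating hemorrhage, stroke and infection or anesthesia into different events is an ordinary classification, and that little escapes it. Symptomatic hemorrhage has its own 90-day event with the same form, narrative and review. Bleeding controlled through the endoscope happens on the treatment day, inside the adverse event window. The control CT is meant to look for re-bleeding, and the core lab measures hemorrhage volume on later scans. A disabling deficit from the sheath is a serious adverse event whatever its mechanism. Sections 7.5.2.1 and 9 give the DSMB all adverse events, not only the named ones. On the windows, 5.9.3 does not limit its list to serious events and Table 1 marks Adverse Events to one year, so the specific rule can be read as overriding the general one. The Manual of Procedures, which is not among the documents, may say more.

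Most of this stands, and it limits the point. It does not remove it. Section 5.9.3 is headed as dealing with serious events, and nothing says that it overrides Section 16. General listings let the DSMB see sub-threshold bleeding, but without a definition they do not yield a rate to set beside 2/29.

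A reader might infer that the protocol leaves bleeding out of its safety events, or that the device's complication rate will be understated. The documents support neither. Symptomatic bleeding is named. No complication rate is an endpoint or has a planned analysis; the primary safety outcome is death within 90 days (Section 7.5.1). A reader might also picture a report of no re-bleeds where several occurred. That would require every re-bleed to be sub-threshold, and the documents give no such split.

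**Conclusion.** The window conflict is real and narrow: it concerns surgical site infections that are both late and non-serious, and only if Section 16 is taken to govern. It is a contradiction to reconcile, not a certain loss of data.

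The coverage gap is also real and limited. Sub-threshold re-bleeding, and a new deficit from access or sheath injury without new blood, infarct or qualifying edema, belong to no named event. For re-bleeding this means 0 to about 3.4 of 50 patients. That range rests on the 6.9% rate carrying over to this trial, on a series whose interval is wide, and on an unknown share below the threshold. Its lower end is none at all. The firm consequence is that the trial's symptomatic-only hemorrhage count cannot be compared like for like with the figure in Section 2.1.

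**What to change.** 1. In Sections 16 and 16.2, state that the named events of 5.9.3 are recorded through day 90 whether serious or not. Extend the visit survey in 5.9.1 from neurological events to all of those named events.
2. From the operative record and the CTs already required (control, post-procedure and day 7), tabulate two further items beside the named events: all re-bleeding, split into symptomatic and not, and any new clinical deficit attributed to the access or sheath path. State that a symptomatic hemorrhage is counted once. Report total re-bleeding, with its exact interval, next to the 2/29 of Section 2.1.

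Keep the second item to clinical deficits. Imaging change along the path, with no threshold set, could flag the track expected from a 19-22F sheath.

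The cost is wording in a few sections, a few extra form fields and a somewhat higher reported complication count. No added visit, scan or patient is needed.
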